## 6.2 Treatment Regimens

Refer to Table 6.2-1 for treatment regimens explored in this trial:

**Table 6.2-1: Treatment Regimen Information**

| Phase       | Treatment Regimen Description                     |
|-------------|---|
| Lead-in     | BMS-986205 100 mg PO QD                           |
| Combination | BMS-986205 100 mg PO QD + Nivolumab 480 mg IV Q4W |

## 6.3 Populations for Analyses

- Enrolled subjects Population: All subjects who signed the informed consent form and obtained a subject number.
- Treated subjects Population: All enrolled subjects who received at least one dose of any study treatment.
- Pharmacokinetic Population: All enrolled subjects who received at least one dose of any study treatment and have any available concentration-time data.
- Evaluable Pharmacokinetic Population: A subset of the PK Population, defined as all subjects who have adequate PK profiles or have at least one evaluable PK parameter. All available derived PK parameter values will be included in the PK data set and reported, but only participants with evaluable PK will be included in the summary statistics.
- Immunogenicity Population: All enrolled subjects who received at least one dose of nivolumab and have a baseline and at least one post-treatment immunogenicity measurement.

Unless otherwise specified, the safety analyses will include all treated subjects.

Unless otherwise specified, the efficacy analyses will include all treated subjects.

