  - On-treatment evaluations (laboratory tests, pulse oximetry and vital signs) will be defined as evaluations taken after the day (and time, if collected and not missing) of first dose of study treatment. For subjects who are off study treatment, evaluations should be within a safety window of 100 days after the last dose of study treatment if a participant received BMS-986205 + NIVO (or 30 days after the last dose of study treatment if a participant received only BMS-986205).

- Post baseline period by phase:
  - Mono lead-in period starts with the first dose of BMS986205 and end prior to first dose of nivolumab.
    - ◆ Mono lead-in AEs will be defined as AEs with an onset date and time on or after the date and time of the first dose of initial mono study treatment (or with an onset date on or after the day of first dose of initial mono study treatment if time is not collected or is missing) and prior to the date-time of the first dose of nivolumab (or with an onset date prior to the day of first dose of nivolumab if time is not collected or is missing). For subjects who discontinue during Mono lead in, AEs will be included if event occurred within a safety window of 30 days after the last dose of BMS-986205 initial mono study treatment. No “subtracting rule” will be applied when an AE occurs both pre-treatment and post-treatment with the same preferred term and grade.
    - ◆ Mono lead-in evaluations (laboratory tests, pulse oximetry and vital signs) will be defined as evaluations taken after the day and time of the first dose of initial mono study treatment (or with a start date after the day of first dose of initial mono study treatment if time is not collected or is missing) and prior to the date-time of the first dose of nivolumab (or with a start date on or prior to the day of first dose of nivolumab if time is not collected or is missing). For subjects who discontinue during Mono lead in, evaluations will be included if evaluation is taken within a safety window of 30 days after the last dose of BMS-986205 initial mono study treatment.
  - Combination Treatment Period starts with the first dose date-time of initial nivolumab.

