    - ◆ Combination treatment AEs will be defined as AEs with an onset date and time on or after the date and time of the first dose of nivolumab (or with an onset date on or after the day of first dose of nivolumab if time is not collected or is missing). For subjects who are off study treatment, AEs will be included if event occurred within a safety window of 100 days after the last dose of study treatment.
    - ◆ Combination treatment evaluations (laboratory tests, pulse oximetry and vital signs) will be defined as evaluations taken after the day (and time, if collected and not missing) of first dose of nivolumab. For subjects who are off treatment, evaluations will be included if evaluation is taken within 100 days of the last dose of study medication.

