### 7.1 General Methods

Unless otherwise noted, discrete variables will be tabulated by the frequency and proportion of subjects falling into each category, grouped by treatment. Percentages given in these tables will be rounded to the first decimal and, therefore, may not always sum to 100%. Percentages less than 0.1 will be indicated as ' $< 0.1$ '. Continuous variables will be summarized using the mean, standard deviation, median, minimum, and maximum values.

Time-to-event variables (e.g., time-to resolution) will be analyzed using the Kaplan-Meier technique. When specified, the median will be reported along with 95% CI using Brookmeyer and Crowley method (using log-log transformation for constructing the confidence intervals).

The conventions to be used for imputing missing and partial dates for analyses requiring dates are described in [Section 8](#).

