#### Subject Phase Status

Number of ongoing, completed and discontinued subjects along with discontinuation reason and next expected study phase will be summarized on the all treated subjects population for the following:

- Mono lead-in
- Combination
- Follow-up (excluding next expected study phase)

Reason for discontinuation will be derived from subject status CRF page.

A by-subject listing including the above information will also be provided for all treated subjects.

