### **7.6 *Safety***

Analyses in this section will be tabulated for all treated subjects by phase (monotherapy lead-in, combination) and overall, unless otherwise specified.

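### Does the SAP need a nivolumab-treated population for its combination-phase safety columns and its response rate?

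*SAP*

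**What the plan says.** SAP Section 6.3 lists five populations. The one used by default for safety and efficacy is: "Treated subjects Population: All enrolled subjects who received at least one dose of any study treatment". One lead-in dose of BMS-986205 is therefore enough to qualify. Only the immunogenicity population requires nivolumab, and it also requires antibody samples.

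For safety, Section 6.3 states: "Unless otherwise specified, the safety analyses will include all treated subjects". Section 7.6 sets the layout: "Analyses in this section will be tabulated for all treated subjects by phase (monotherapy lead-in, combination) and overall, unless otherwise specified". Section 6.1 defines the phases: "Combination Treatment Period starts with the first dose date-time of initial nivolumab". A combination-phase adverse event is accordingly one of the "AEs with an onset date and time on or after the date and time of the first dose of nivolumab". Section 7.1 says that "discrete variables will be tabulated by the frequency and proportion of subjects falling into each category, grouped by treatment", and Table 6.2-1 describes the combination regimen as "BMS-986205 100 mg PO QD + Nivolumab 480 mg IV Q4W".

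For efficacy, SAP Sections 4.1.1 and 7.5.1 divide responders by all treated subjects. The related secondary objective (SAP Section 3.2) concerns activity of the two drugs together.

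**The concern.** The numerator of the combination column can come only from people who received nivolumab. If the Section 6.3 default also fixes the denominator, that column would count people who were never at risk in the phase. The design expects some of them. Protocol Section 5.1 lists Cycle 0 events that bar entry to Cycle 1, requires at least 75% of Cycle 0 doses before Cycle 1, and gives participants who received only BMS-986205 a single follow-up visit. Protocol Section 5.2 replaces participants who discontinue before or at Cycle 1 Day 1, so more than 12 people may be treated.

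Adverse event incidence is a primary endpoint, and an inflated denominator understates it, which is the wrong direction for safety.

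The response rate raises a milder form of the same worry. Lead-in-only participants have no scheduled scan in Cycle 0, the first planned on-treatment scan is at the end of Cycle 2, and a response must be confirmed at least 4 weeks later. They are almost certain to count as non-responders to a combination they did not receive.

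**Working it through.** **1. The plan's own figure.** SAP Section 5 says 12 subjects give a 90% probability of seeing at least one event of 18% incidence. The calculation is 1 − (1 − 0.18)^12 = 1 − 0.82^12 = 0.908, which agrees. It is a design statement about 12 subjects and does not depend on the N printed in a safety table.

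**2. Size of the effect if N were all treated.** Let n be the number given nivolumab and r the number who received only the lead-in. Take n = 12, with lead-in stoppers replaced under Protocol Section 5.2. The documents give no r, so 0 to 4 is assumed. Every combination-phase percentage is multiplied by n/(n + r). The last two columns show examples with 6 participants having a given event and with 3 responders.

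| r | n + r | factor | 6 with an event | 3 responders (exact 95% CI) |
|---|---|---|---|---|
| 0 | 12 | 1.000 | 50.0% | 25.0% (5.5 to 57.2) |
| 1 | 13 | 0.923 | 46.2% | 23.1% (5.0 to 53.8) |
| 2 | 14 | 0.857 | 42.9% | 21.4% (4.7 to 50.8) |
| 3 | 15 | 0.800 | 40.0% | 20.0% (4.3 to 48.1) |
| 4 | 16 | 0.750 | 37.5% | 18.8% (4.0 to 45.6) |

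For the event example the shift is 50.0 − 46.2 = 3.8 points at r = 1 and 50.0 − 37.5 = 12.5 points at r = 4. For response it is 25.0 − 23.1 = 1.9 points at r = 1 and 25.0 − 18.75 = 6.25 points, or 6.3, at r = 4. The exact interval for 3 of 12 is 57.2 − 5.5 = 51.7 points wide.

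**3. Which N the text supports.**

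- Section 7.6 asks for tables by phase as well as overall. A separate overall column is where all treated participants belong.
- Section 7.1 groups proportions by treatment, and Table 6.2-1 gives the combination phase its own regimen. A person who never had nivolumab was not on that regimen.
- Section 6.1 has a rule for people who discontinue in the lead-in. Their events stay in the lead-in phase, with a 30-day window after the last dose. The SAP foresaw these participants and assigned them to that phase. The rule governs events and does not itself state N, but it fits a phase-specific N.
- Section 7.4 assesses exposure separately for the lead-in and for the combination, and Section 7.4.1 summarizes it by phase and study therapy. The number exposed to nivolumab should therefore be evident.
- On the other side stands the literal Section 6.3 default. The phase-status table in Section 7.3.1, which has a combination row, "will be summarized on the all treated subjects population for the following". That table reports disposition: who completed, who discontinued and which phase comes next. All treated is its natural base, and it says nothing about event denominators.

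**4. Whether a wrong choice could stay hidden.** Section 7.1 requires frequencies beside proportions, and the counts do not change with N. The phase-status table in Section 7.3.1 shows how many entered the combination. The by-subject event listing in Section 7.6.5 allows recalculation. Laboratory tables (Section 7.6.10) are restricted to treated subjects who had the test. The sponsor's safety review in Protocol Section 7.4 concerns patients given both drugs and sets no percentage threshold.

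**The case for a change.** The strongest argument for a change is that analysis populations belong in SAP Section 6.3. That section defines a nivolumab-based set for immunogenicity, yet leaves a primary-endpoint column to a default that, taken at its word, covers people outside the phase. The wording needed would be short, no new data would be collected, and the possible error runs in the anti-conservative direction. The Data Presentation Plan, to which SAP Section 9 defers the list of analyses, is not available here, so nobody can confirm that it fixes the table Ns.

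Much of this stands. The SAP does not state N for the combination column, and a programmer following only the Section 6.3 sentence could use all treated. At r = 4 the resulting distortion would not be trivial.

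What does not stand is the step from an unstated N to a wrong one. No sentence places lead-in-only participants in the combination column, and the provisions on phase, treatment and exposure lead an analyst to the other reading.

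The argument on response rate is weaker still. The denominator is fixed in advance and errs toward a lower rate. Every participant starts with the lead-in, so all treated is a fair base for the planned regimen. A rate among those given nivolumab would be conditional on getting through the lead-in, which brings its own selection. Protocol Section 10.3.1 leaves the denominator to the population of interest, and the SAP has chosen one openly.

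**Conclusion.** No change to the plan is called for. The combination-column N is a missing detail that analysts would fill sensibly with the participants who received nivolumab, possibly in the Data Presentation Plan. Harm would require three things together: at least one participant stopping in the lead-in, the literal reading of the default, and a reader who ignores the counts and the disposition table. In that case percentages would fall by a relative 7.7% at r = 1 (1 − 12/13) to 25% at r = 4 (1 − 12/16). At r = 0 nothing changes. These sizes rest on the assumptions n = 12 and r between 0 and 4.

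The all-treated response rate is an acceptable, pre-stated choice. A second version would move the estimate by 1.9 to 6.3 points in the 3-responder example, well inside its interval, for a secondary endpoint with no decision threshold.

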## 7 STATISTICAL ANALYSES

All analyses will be performed in SAS using version 9.3 or higher and S-Plus for some figures.

### 7.1 General Methods

Unless otherwise noted, discrete variables will be tabulated by the frequency and proportion of subjects falling into each category, grouped by treatment. Percentages given in these tables will be rounded to the first decimal and, therefore, may not always sum to 100%. Percentages less than 0.1 will be indicated as ' $< 0.1$ '. Continuous variables will be summarized using the mean, standard deviation, median, minimum, and maximum values.

Time-to-event variables (e.g., time-to resolution) will be analyzed using the Kaplan-Meier technique. When specified, the median will be reported along with 95% CI using Brookmeyer and Crowley method (using log-log transformation for constructing the confidence intervals).

The conventions to be used for imputing missing and partial dates for analyses requiring dates are described in [Section 8](#).

### **7.1.1 Adverse Events, Serious Adverse Events, Multiple events, Select Adverse Events, [REDACTED] and Immune-Mediated Adverse Events**

Drug-related AEs are those events with relationship to study drug “Related”, as recorded on the CRF. If the relationship to study drug is missing, the AE will be considered as drug-related.

Serious adverse events consist of AEs deemed serious by the Investigator and flagged accordingly in the CRF and clinical database.

Adverse events leading to study drug discontinuation are AEs with action taken regarding study drug(s) = “Drug Withdrawn”.

Adverse events leading to dose delay are AEs with action taken regarding study drug(s) = “Dose Delayed”.

[figure not shown]
Adverse events leading to dose reduction are AEs with action taken regarding study drug(s) = “Dose Reduced”.

Adverse events will be coded using the Medical Dictionary for Regulatory Activities (MedDRA), and the most recent version of the dictionary at the time of the database lock will be used. Adverse event results will be graded for severity using the NCI Common Terminology Criteria for Adverse Events (CTCAE) and the version of the criteria specified in the protocol will be used.

In the AE summary tables, unless otherwise specified, subjects will be counted only once at the Preferred Term (PT), only once at the System Organ Class (SOC), and only once at subject level for the counting of total number of subjects with an AE. The AE tables will be sorted by the SOCs and then PTs. SOC will be ordered by descending frequency overall and then alphabetically. PTs will be ordered within SOC by descending frequency overall and then alphabetically. The sorting will be done based on the ‘Any Grade’ column.

Unless otherwise specified, the AE summary tables will be restricted to on-treatment events regardless of the causality.

Analyses that take into account the multiple occurrences of a given adverse event will be conducted (see [Section 7.6.9](#)). To prepare these analyses, the CRF data will be processed according to standard BMS algorithms in order to collapse adverse event records into unique records based on the preferred term.

#### **7.1.1.3 *Immune-Mediated Adverse Events (US Submission)***

In order to further characterize AEs of special clinical interest, analysis of immune-mediated AEs (IMAE) will be conducted. IMAEs are specific events (or groups of PTs describing specific events) that include pneumonitis, diarrhea/colitis, hepatitis, nephritis/renal dysfunction, rash, endocrine (adrenal insufficiency, hypothyroidism/thyroiditis, hypothyroidism, thyroiditis, hyperthyroidism, diabetes mellitus, and hypophysitis), and other specific events, considered as potential immune-mediated events by investigator that meet the definition summarized below:

- those occurring within 100 days of the last dose
- regardless of causality
- treated with immune-modulating medication (of note, endocrine AEs such as adrenal insufficiency, hypothyroidism/thyroiditis, hypothyroidism, thyroiditis, hyperthyroidism, diabetes mellitus, and hypophysitis are considered IMAEs regardless of immune-modulating medication use, since endocrine drug reactions are often managed without immune-modulating medication)
- with no clear alternate etiology based on investigator assessment, or with an immune-mediated component

The list of MedDRA preferred terms used to identify IMAEs is revisited quarterly and updated accordingly. The preferred terms used for the selection at the time of the database lock by categories will be provided.

#### **7.1.2 *Laboratory Tests***

Clinical laboratory parameters (hematology, serum chemistry and electrolytes) will be evaluated.

Laboratory tests will be graded using the NCI Common Terminology Criteria, and the most recent version of the criteria at the time of the database lock will be used.

Clinical laboratory data will be first analyzed using International System of Units (SI).

Analyses will be repeated using US conventional units.

In the laboratory summary tables, unless otherwise specified, subjects will be counted only once for each lab parameter according to their worst on treatment CTC grade (worst being the highest CTC grade). The laboratory tables and listings will be sorted by laboratory category, laboratory subcategory and laboratory test code sequence number.

### **7.1.3 *Immunogenicity data***

Blood samples for nivolumab immunogenicity analysis will be collected according to the protocol schedule. Samples will be evaluated for development of Anti-Drug Antibody (ADA) by a validated electrochemiluminescent (ECL) immunoassay.

## **7.2 *Study Conduct***

Non-programmable relevant eligibility and on-treatment, as well as significant (both programmable and/or non-programmable) protocol deviations will be reported through [REDACTED] listings.

Enrollment by country and site will be summarized and listed for all enrolled subjects.

A by-subject listing of batch numbers for all treated subjects will be provided.

## **7.3 *Study Population***

Analyses in this section will be tabulated for all treated subjects, unless otherwise specified.

### **7.3.1 *Subject Disposition***

#### Subject Pre-treatment Status

The total number of subjects enrolled (entering or not entering treatment period) will be presented along with the reason for not entering treatment period. This analysis will be performed on the all enrolled subjects population only.

Reason for not entering treatment period will be derived from subject status CRF page.

A by-subject listing including the above information will also be provided for all enrolled subjects.

#### Subject Phase Status

Number of ongoing, completed and discontinued subjects along with discontinuation reason and next expected study phase will be summarized on the all treated subjects population for the following:

- Mono lead-in
- Combination
- Follow-up (excluding next expected study phase)

Reason for discontinuation will be derived from subject status CRF page.

A by-subject listing including the above information will also be provided for all treated subjects.

### Subject Completion Status

Number of subjects of the following along with discontinuation reason will be summarized on the all treated subjects population:

- Ongoing
- Completed the study
- Discontinued the study
- Reason for discontinuation will be derived from subject status CRF page.

A by-subject listing including the above information will also be provided for all treated subjects.

### **7.3.2 Demographics and Other Baseline Disease Characteristics**

The following demographic and baseline disease characteristics will be summarized and listed:

- Age (continuous)
- Age categorization (< 65, ≥ 65)
- Sex (Male vs. Female)
- Race (White, Black or African American, Asian, American Indian or Alaska Native, Native Hawaiian or Other Pacific Islander, Asian Indian, Chinese, Japanese, Malay, Asian Other, Other)
- Height
- Baseline Weight
- Baseline ECOG performance status
- Smoking History (Current/Former, Never Smoked - listed only)
- Disease characteristics (listed only):
  - Tumor type
  - For Melanoma: stage and disease classification at initial diagnosis; stage and disease classification at study entry
  - For NSCLC: stage, disease classification and cell type at initial diagnosis; stage and disease classification at study entry
  - For RCC: stage and cell type at initial diagnosis; stage and disease classification at study entry
  - For Bladder Cancer: stage, disease classification, location and minor histological variants at initial diagnosis; stage, disease classification and location at study entry
  - For CRC: stage, disease classification, cell type and location at initial diagnosis; stage and disease classification at study entry
  - For SCLC: stage and cell type at initial diagnosis; stage and disease classification at study entry
  - For Breast Cancer: stage, disease classification and cell type at initial diagnosis; stage and disease classification at study entry
  - For Pancreatic Cancer: stage and cell type at initial diagnosis; stage and disease classification at study entry

- For Hepatocellular Carcinoma: stage and cell type at initial diagnosis; stage at study entry
- For Head and Neck: stage, cell type and location at initial diagnosis; stage at study entry
- For Gastric Cancer: stage at initial diagnosis; disease classification and cell type at study entry
- For Esophageal Cancer: stage at initial diagnosis; disease classification, cell type and location at study entry
- For Gastroesophageal Junction: stage at initial diagnosis; disease classification and cell type at study entry
- For Other Solid Tumors: stage and cell type at initial diagnosis; stage and disease classification at study entry

### **7.3.3 *Medical History***

A by-subject listing of general medical history for all treated subjects will be provided.

